4.5 Secondary Analysis of CAE30

The first secondary endpoint “composite adverse events until day 30” (CAE30) will be analyzed for safety non-inferiority of the PCT arm vs. the Control arm on the basis of the PP patient population. The analysis will also be conducted on the basis of the ITT patient populations and ITT- and PP-results will be compared and discussed. Differences in proportions of CAE30 between PCT arm and Control arm will be assessed by Bayesian analysis assuming binomially distributed events. Posterior probabilities will be computed study-arm specifically using conjugate beta-distributed and

uninformative uniform priors (shape parameters $\alpha = \beta = 1$). More specifically, the following generative model will be used:

$$\begin{aligned} NE_{PCT} &\sim \text{Binomial}(N_{PCT}, p_{PCT}) \\ NE_{ctrl} &\sim \text{Binomial}(N_{ctrl}, p_{ctrl}) \\ \text{priors: } p_{PCT}, p_{ctrl} &\sim \text{Uniform}(0, 1) \end{aligned}$$

with

NE_{PCT}, NE_{ctrl} : number of patients with CAE30 of the PCT arm and Control arm, respectively

N_{PCT}, N_{ctrl} : number of patients randomized to the PCT arm and Control arm, respectively

p_{PCT}, p_{ctrl} : CAE30 probability for patients of the PCT arm and Control arm, respectively

Differences between beta-distributed study-arm specific CAE30 posterior probabilities will be computed by Monte Carlo simulation sampling CAE30 probabilities p_{PCT}, p_{ctrl} from their analytically computed study-arm specific posterior probabilities. Study success is specified by more than $\gamma = 0.985$ posterior probability for a CAE30 probability of patients of the PCT arm smaller than the CAE30 probability of the Control arm plus $M = 10\%$ (NI margin):

$$\text{Probability(CAE30 probability of PCT arm} < \text{CAE30 probability of Control arm} + M \text{)} > \gamma ,$$

or with the above introduced notation

$$\text{Probability(} p_{PCT} < p_{ctrl} + M \text{)} > \gamma .$$

See Section 2.3 for the computation of the parameter γ which was set to $\gamma = 0.985$.

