8.4 Analysis Populations

The intention-to-treat (“**ITT**”) patient population will comprise all randomized non-COVID-19 patients.

The per-protocol (“**PP**”) patient population will comprise all ITT patients

- (a) fulfilling study inclusion criteria,
- (b) not meeting study exclusion criteria at enrollment,
- (c) even if meeting study exclusion criterion after enrollment or meeting a pre-defined overruling criterion,

- (d) with PCT measurements performed daily in the first week and thereafter at least every 48 hours during hospitalization and antibiotic treatment,
- (e) if assigned to PCT group, antibiotic steward ship team recommendation given to the treating physician on enrollment day and for each PCT measurement taken Monday-Friday described under d) and antibiotics stopped according to the PCT algorithm. An exception will be made if the stewardship team decides the patient will be given the same recommendation throughout their hospitalization.

Consequently, it should be noted that stewardship team recommendations should also be provided for patients meeting pre-defined overruling criteria (e.g., need for ICU care) since such patients may still qualify for the per-protocol population.

Patients of the PCT arm who are discharged before that day's PCT has resulted will be excluded from the per protocol population. Patients in the PCT arm who were continued on antibiotics despite a weekend/holiday/no stewardship team member available PCT value that would have resulted in an stewardship team recommendation to stop antibiotics will also be excluded from the per protocol population. Patients in the PCT arm whose antibiotics were discontinued despite weekend/holiday/no stewardship team member available PCT value that would have resulted in continuation of antibiotics will also be excluded.

- (f) if assigned to control group, no PCT measurements to treating physician during index hospitalization.

Primary analysis of the superiority endpoint “antibiotic exposure” will be conducted on the basis of the ITT patient population. Analysis of the non-inferiority endpoint “composite adverse events until day 30” will be conducted on the basis of PP and ITT patient population. PP-results will be compared and discussed with corresponding results obtained for ITT patient population.

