8.6.3 Secondary Analysis of CAE30

The first secondary endpoint “composite adverse events until day 30” (CAE30) will be analyzed for safety non-inferiority of the PCT arm vs. the control arm on the basis of the PP patient population. The analysis will also be conducted on the basis of the ITT patient populations and ITT- and PP-results will be compared and discussed. Differences in proportions of CAE30 between PCT arm and control arm will be assessed by Bayesian analysis assuming binomially distributed events (beta-distributed study-arm specific CAE30 probabilities) and uninformative uniform priors. More specifically, the following generative model will be used:

$$NE_{PCT} \sim \text{Binomial}(N_{PCT}, p_{PCT})$$

$$NE_{ctrl} \sim \text{Binomial}(N_{ctrl}, p_{ctrl})$$

$p_{PCT}, p_{ctrl} \sim \text{Uniform}(0, 1)$

with

NE_{PCT}, NE_{ctrl} : number of patients with CAE30 of the PCT arm and control arm, respectively

N_{PCT}, N_{ctrl} : number of patients randomized to the PCT arm and control arm, respectively

p_{PCT}, p_{ctrl} : CAE30 probability for patients of the PCT arm and control arm, respectively

Differences between study-arm specific CAE30 probabilities will be computed by Monte Carlo simulation sampling CAE30 probabilities p_{PCT}, p_{ctrl} from their analytically computed study-arm specific posterior probabilities. Study success is specified by more than 98.5%¹ posterior probability for a CAE30 probability of patients of the PCT arm smaller than the CAE30 probability of patients of the control arm plus 10% (NI margin):

Probability(CAE30 probability of PCT arm < CAE30 probability of control arm + 10%) > 98.5% ¹,

or with the above introduced notation

Probability($p_{PCT} < p_{ctrl} + 0.1$) > 98.5% ¹.

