The protocol changes required a re-specification of the analysis parameter γ to assure type-I error rate control at 2.5% (new order of hierarchical testing of endpoints: first shortABx, then CAE30, then prescribedABx; null hypothesis for shortABx instead of CAE30; interim and final CAE30 NI analyses on PP populations; interim analyses with 550 and 650 patients). Under the null for the primary study endpoint shortABx (relative risk of shortABx for PCT arm versus Control arm set to 1) and under the additional conservative assumptions of effects of CAE30 and prescribedABx as in the pilot study ($RR_{CAE30} = 0.30$, $RR_{prescribedABx} = 0.60$; PCT arm versus Control arm) and the PP population as a random subset of 50% of the patients of the full population (50% estimated for the running study), a γ value of 0.985 was determined to keep the type-I error rate below 2.5% (increase of γ vs. previous protocol version from 0.9785 to 0.985; γ estimated by linear regression of type-I error rate vs. specified γ values based on Monte Carlo runs with 50,000 simulated clinical trials).

Moreover, simulations showed that adequate statistical power could be achieved even for small CAE30 effects. Assuming (a) half of the shortABx effect observed in the pilot study ($RR_{shortABx} = 1.9$), (b) only one tenth of the CAE30 effect observed in the pilot study ($RR_{CAE} = 0.9$), (c) half the prescribedABx effect observed in the pilot study ($RR_{prescribedABx} = 0.80$), and (d) the PP population as a random subset of 50% of the patients of the full population (50% PP patients estimated for the running study), we obtained 99% statistical power for shortABx superiority on ITT population, 75%

for CAE30 non-inferiority on PP population, and 48% for prescribedABx superiority on ITT population. The following Table 2.6 gives an overview of the study design characteristics of this scenario.

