Table 2.6: Characteristics of the study design with protocol changes (sABx as primary endpoint, CAE30 non-inferiority testing with 10% NI margin, IA with 550 and 650 patients, and $\gamma = 0.985$) assuming (a) half the effect observed in the pilot study for shortABx ($RR_{shortABx} = 1.9$), (b) only one tenth of the CAE30 effect observed in the pilot study ($RR_{CAE} = 0.9$), (c) half the effect observed in the pilot study for prescribedABx ($RR_{prescribedABx} = 0.80$), and (d) the PP population as a random subset of 50% of the patients of the full population. Interim, final and total results in rows, first two columns to describe the level of analysis, columns three to five for the probabilities of meeting endpoint-specific study success criteria (hierarchical testing: (1) shortABx superiority on ITT population, (2) CAE30 non-inferiority on PP population, (3) prescribedABx superiority on ITT population, columns six to eight for outcomes of interim analyses.

Abbreviations: “IA” for “interim analysis”, “IA-200” for “IA with 200 enrolled patients”, “End-700” for “final analysis with 700 enrolled patients”, “-” for “not applicable” and “recom.” for “recommendation”.

Level of Analysis		Results						
Stage of Analysis	# PP Patients	Probability of Meeting EP Success Criteria			Interim Analysis Outcome			Efficacy
		sABx	CAE30	pABx	Futility recom.	Study stopped		
IA-200	100	-	-	-	7%	-	0%	
IA-350	176	-	-	-	8%	-	0%	
IA-550	276	27%	27%	27%	12%	27%	27%	
IA-650	324	12%	12%	12%	15%	12%	12%	
End-700	350	59%	36%	9%	-	-	-	
Total	-	99%	75%	48%	-	39%	39%	

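### CAE30 non-inferiority, and with it the gate to prescribedABx, is decided on the per-protocol set alone; require ITT and per-protocol to agree, at interim and final

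*SAP*

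**What the plan says.** SAP 4.5 states that CAE30 "will be analyzed for safety non-inferiority of the PCT arm vs. the Control arm on the basis of the PP patient population". Protocol 8.6.3 has the same rule. Both also run the ITT analysis, but only so that "ITT- and PP-results will be compared and discussed"; nothing says what follows if the two disagree. Protocol 8.4 and SAP 3.1 put it differently: the CAE30 analysis "will be conducted on the basis of PP and ITT patient population", again without a decision rule. SAP 2.4 and 4.6 open the prescribedABx test only after CAE30 non-inferiority is concluded.

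The design simulations follow the PP reading. SAP 2.3.3 lists "interim and final CAE30 NI analyses on PP populations" and takes "the PP population as a random subset of 50% of the patients of the full population". Table 2.6 reports CAE30 on PP and gives PP counts at every look. The success threshold was found "Under the null for the primary study endpoint shortABx", with CAE30 set at a relative risk of 0.30.

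Two passages do not fit. SAP 4.5 defines its denominators as the "number of patients randomized to the PCT arm and Control arm, respectively", although the analysis is placed on PP. Protocol 8.9 and SAP 2.5 name no analysis set for the interim CAE30 rules, and SAP 2.5 projects to 350 patients per arm, which is full enrolment.

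**The concern.** PP membership depends on what happens after randomisation, and the filters differ by arm. Clause (d), on PCT measurement frequency, applies to both arms, and clause (f), on PCT results reaching the physician, to controls. The filters on how care was delivered apply to the PCT arm only: recommendations given, antibiotics stopped according to the algorithm, discharge before that day's PCT result, and antibiotic handling on days without stewardship cover. The only formal safety claim therefore compares two groups, about half of those enrolled, that randomisation no longer makes comparable.

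If PCT-arm patients who drop out of PP are at higher risk than those who stay, PP can show non-inferiority that the randomised comparison would not support. The ITT result would be published alongside it but would change neither the declaration nor the opening of the prescribedABx test. The plan's type-I error statement does not cover this case: it concerns the shortABx null, with CAE30 strongly favourable and PP a random subset.

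**Working it through.** **Inputs.** Uniform priors, margin 0.10, threshold 0.985 (SAP 4.5). Maximum 350 per arm, PP share 50%, so 175 per arm in PP. Overall rates: CAE30 20%, shortABx 22%, prescribedABx 40%. Relative risks: 0.9, 1.9 and 0.8 (SAP 2.3.3). Success stop at 550 and 650 if the predictive probability exceeds 0.9 for all three endpoints; futility non-binding (SAP 2.5).

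**Reproducing the stated 75% CAE30 power.** A relative risk of 0.9 with a 20% average gives 0.40/1.9 = 21.05% (control) and 18.95% (PCT). SE = √[(0.2105×0.7895 + 0.1895×0.8105)/175] = 0.0427. Power = Φ[(0.10 + 0.0211)/0.0427 − 2.170] = 74.6%. The exact beta-binomial rule gives 74.9%.

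Two simulations of the whole design, with looks and hierarchy, against the stated 99% / 75% / 48%:
- Simulation A (300,000 trials per scenario, posteriors integrated numerically, about 12 patients per arm pending at each look): 99% / 74.4% / 44.8%; early stops 18% and 11%.
- Simulation B (10,000 to 40,000 trials per setting, normal approximation to the posterior, CAE30 times uniform over 30 days): 98.9% / 74.5% / 46.0%; early stops 24% and 12%.

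Table 2.6 has early stops of 27% and 12%, so both only approximate the plan's simulation.

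**False non-inferiority at the margin.** Take true CAE30 risks of 30% (PCT) and 20% (control). If excluded PCT patients have *r* times the risk of retained ones, the PCT risk within PP is 0.60/(1 + *r*). With equally selective exclusion of controls, the control risk within PP is 0.40/(1 + *r*). Results for PP alone, from simulation A, with the exact single-look value in brackets:

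| *r* (assumed) | PCT risk in PP | Controls excluded at random | Controls equally selected |
|---|---|---|---|
| 0.8 | 33.3% | 0.2% (0.2%) | – |
| 1.0 | 30.0% | 1.6% (1.6%) | 1.6% (1.6%) |
| 1.25 | 26.7% | 8.2% (7.9%) | 3.0% (2.9%) |
| 1.5 | 24.0% | 22% (21%) | 4.9% (4.6%) |
| 2.0 | 20.0% | 57% (57%) | 9.6% (9.3%) |

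With pilot-size antibiotic effects and random PP the figure is 1.9%. ITT gives 1.5% to 1.7% (1.9% with pilot-size effects). Requiring both sets gives 0.1% to 1.6%.

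Simulation B, at 25% v 15% and with PP shifted in favour of the PCT arm by 2.5, 5, 7.5 or 10 points (assumed), gives 7.6%, 21%, 42% and 70% on PP alone, and at most 2.0% with both required. With random PP it gives 2.05% to 2.1%.

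**Is the pilot PP set random?** Table 8.1, ITT minus PP, taking PP as a subset; Fisher's exact test, unadjusted:

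| Endpoint, arm | In PP | Outside PP | p |
|---|---|---|---|
| CAE30, PCT | 1/30 | 2/18 | 0.55 |
| CAE30, control | 7/30 | 3/17 | 0.73 |
| shortABx, PCT | 12/30 | 2/18 | 0.049 |
| shortABx, control | 3/30 | 2/17 | 1.0 |
| prescribedABx, PCT | 7/30 | 8/17 | 0.11 |
| prescribedABx, control | 19/29 | 5/17 | 0.03 |

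There is a hint of selection on antibiotic endpoints and none detectable on CAE30.

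**Interim.** Suppose that at 550 enrolled the complete CAE30 data are 59/263 (PCT) v 46/263 (control). Projected to 350 per arm, the predictive probability of success is 0.20. Similar rates on PP, 30/132 v 23/132, projected to 175 per arm give 0.03. The futility cut-off is 0.1, so the choice of set decides the recommendation. The example is sensitive: with 28/132 in the PCT arm the PP value is 0.11.

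**The case against.** The best defence has four parts.

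- Under the plan's own model nothing is breached: with random PP the error is 1.6% to 2.1%, below 2.5%. PP is then usually the stricter set. In the plan's scenario ITT passes while PP fails in 22% of trials, and the reverse happens in 0.5%.
- The large error figures rest on assumed risk ratios that no document supplies. At a ratio of 2.0 with random control exclusion, both PP arms have a true risk of 20%, so the whole excess lies outside PP; that is an extreme.
- The pilot is weak evidence. Neither small p-value survives correction for six contrasts (0.05/6 = 0.0083), and the shortABx contrast may follow mechanically from clause (e). PP was respecified in SAP version 2, after the pilot had ended, and the pilot left out patients moved to ICU within 24 hours.
- Protocol 8.4 and SAP 3.1 name both sets, SAP 2.3.3 does state PP for the interim looks, and futility is non-binding.

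All of this is right on the facts and limits what can be claimed: PP has not been shown to be biased. It does not supply a rule for discordant results, a reported CAE30 error at the margin, or a consistent interim definition.

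**Conclusion.** The concern holds. As written, the safety claim and the gate to prescribedABx are decided on PP alone, and the error of that claim at the 10-point margin is not reported. It is below 2.5% if PP is a random subset, and lower still if selection runs against the PCT arm (0.2% at a ratio of 0.8). It exceeds 2.5% under quite modest selection in the PCT arm's favour: 8.2% at a ratio of 1.25 with random control exclusion, 3.0% if controls are selected equally. Neither the size nor the direction of selection can be read from the documents, so these figures show exposure, not an expected error rate. The textual points do not depend on any assumption: the decision rule, the conflict between sections, the denominators and the unnamed interim set.

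**What to change.** 1. In Protocol 8.6.3 and SAP 4.5, declare CAE30 non-inferiority only if the posterior probability exceeds 0.985 in both ITT and PP, and test prescribedABx only then. Align Protocol 8.4 and SAP 2.4, 3.1 and 4.6.
2. Define the SAP 4.5 denominators as the patients in the set being analysed.
3. Use the same both-sets definition of CAE30 success in the futility and success rules of Protocol 8.9 and SAP 2.5, and state the set sizes in the prediction steps.
4. Re-run the simulations behind Table 2.6 and the stated 75% and 48% powers (also in Protocol 8.8), and report the CAE30 error at the 10-point margin.

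**Cost.** Wording and one re-simulation; no new data, since both analyses are already planned. With random PP (simulation A), CAE30 power falls from 74.4% to 74.0% at relative risk 0.9 and from 57.0% to 55.8% at 1.0. prescribedABx power falls from 44.8% to 44.6% and from 34.3% to 33.5%.

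If PP favours the PCT arm (ratios 1.25 to 2.0), CAE30 power falls by 1.1 to 2.8 points at relative risk 0.9 and by 3.9 to 10.5 at 1.0; prescribedABx falls by 0.7 to 1.7 and by 2.4 to 6.4. At a true excess of 2 points with a 5-point PP shift, simulation B has CAE30 power falling from 85% to 65%. That loss is the price of the protection. With a ratio of 0.8 the cost is about 0.1 points at relative risk 0.9.

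The rule limits false declarations; it does not remove bias from the PP estimate itself.

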4.6 Secondary Analysis of Antibiotic Exposure

The second secondary endpoint “antibiotic exposure at discharge” will be analyzed for superiority. We will assess the differences in proportions by Bayesian analysis assuming binomially distributed events. Posterior probabilities will be computed study-arm specifically using conjugate beta-distributed and uninformative uniform priors (shape parameters $\alpha = \beta = 1$). More specifically, the same generative model will be used as the one for short antibiotic treatments (see Section 4.4). Differences between beta-distributed study-arm specific posterior probabilities will be computed by Monte Carlo simulation with sampling from study-arm specific posterior probabilities. Success of the analysis of antibiotic exposure at discharge is specified by more than $\gamma = 0.985$ posterior probability for less antibiotic exposure of the PCT arm than of the Control arm, i.e., more than $\gamma = 0.985$ probability that prescriptions of antibiotics for pneumonia are less probable for patients of the PCT arm than for patients of the Control arm:

$$\text{Probability[prob(discharge-ABx | PCT arm)} < \text{prob(discharge-ABx | Control arm)} \text{]} > \gamma$$

with

$\text{prob(discharge-ABx | PCT arm)}$: probability of prescribed antibiotics at hospital discharge for patients randomized to the PCT arm,

$\text{prob}(\text{discharge-ABx} | \text{Control arm})$: probability of prescribed antibiotics at hospital discharge for patients randomized to the Control arm,

$$\gamma = 0.985.$$

The endpoints will be tested in a hierarchical manner: first, superiority testing will be conducted for the primary endpoint shortABx (see Section 4.4). If superiority is concluded for shortABx, then non-inferiority testing will be conducted for the first secondary endpoint CAE30 (see Section 4.5). If non-inferiority is concluded for CAE30, then superiority testing will be conducted for the second secondary endpoint prescribedABx. This hierarchical testing scheme allows to test the three endpoints without correction for multiple testing.

4.7 Sensitivity Analysis

Sensitivity analysis will be conducted to assess the robustness of primary and secondary analysis results.

- The results obtained for ITT and PP patient population will be compared and discussed.
- Differences between study-arm-specific posterior probabilities will also be determined by the following Bayesian MCMC analysis adjusting effects between study arms for covariate “site” (used for stratifying randomization). The primary study endpoint (shortABx) and the first two secondary study endpoints (CAE30, prescribedABx) will be assumed to be distributed binomially

$$\text{endpoint} \sim \text{Binomial}(1, p),$$

with probability “p” parameterized by a global intercept “a”, site-specific intercepts “ b_{site} ” and study-arm specific intercepts “ c_{arm} ”

$$\text{logit}(p) = a + b_{\text{site}} + c_{\text{arm}},$$

using uninformative priors

$$\begin{aligned} a &\sim \text{Normal}(m = 0, \sigma = 1.5), \\ b_{\text{site}} &\sim \text{Normal}(m = 0, \sigma = 0.5), \\ c_{\text{arm}} &\sim \text{Normal}(m = 0, \sigma = 0.5), \end{aligned}$$

with mean m and standard deviation σ .

Probabilities for superiority of the PCT arm vs. the control arm (shortABx, prescribedABx) will be determined from the posterior sampling distributions of model parameters c_{PCT} and c_{control} : Samples will be drawn for c_{PCT} and c_{control} from their posterior distributions, the proportion of sample pairs fulfilling the criterion $c_{\text{PCT}} > c_{\text{control}}$ (for higher probability of short antibiotic treatment in the PCT-arm vs. the control-arm) or $c_{\text{PCT}} < c_{\text{control}}$ (for lower probability of antibiotics prescribed at discharge in the PCT-arm vs. the control-arm) will be determined, and it will be assessed if the obtained proportion is above $\gamma = 0.985$ fulfilling the endpoint-specific study success criterion.

Probabilities for non-inferiority of the PCT arm vs. the control arm (CAE30) will be determined similarly but will additionally include patient bootstrap sampling from the study population and evaluation of the CAE30 success criterion on the level of probabilities for applying the non-inferiority margin $M = 10\%$: (a) draw patient site “i” from study population with replacement, (b) draw samples for model parameters b_i , c_{PCT} and c_{control} from posterior probability distributions, (c)

4.8 Further Secondary and Exploratory Analysis

Secondary and exploratory endpoints will be analyzed according to variable type:

Numerical endpoints:

Distributions of numerical variables will be visualized for all patients and separately for PCT and Control arm. Study arm-specific distributions will be compared with each other by statistical tests (e.g. Wilcoxon rank-sum tests), and by comparing descriptive summary measures (e.g. group medians and means).

Binary endpoints:

2 x 2 contingency tables will be reported for counts stratified according to study arm (PCT, control) and endpoint level (true/false). Associations between study arms and endpoints will be analyzed by statistical tests (e.g. chi-square test or Fisher's exact test). Proportions and two-sided 95% confidence intervals or Bayesian credible intervals will be computed for all patients and separately for PCT and Control arm.

